8.4 Statistical Methods

The primary efficacy endpoint is the occurrence of a treated relapse within 24 months after completion of initial treatment. The non-inferiority of the experimental group *vs.* control group will be evaluated using the test according to Farrington and Manning [17]. The one-sided significance level is set to 5%.

The hypotheses to be assessed in the primary efficacy analysis are formulated as follows: H_0 : $p_MMF - p_Prednisone \ge \delta$ (δ =0.15, non-inferiority margin, see Section 8.1 Sample Size Calculation for justification)

 H_1 : p_MMF – p_Prednisone < δ , where p_* denotes the relapse rate in the respective group.

Before database closure the assignment of patients to the PP population (patients with no major protocol violations) and the ITT population (as classified by the intent-to-treat principle) are defined in the statistical analysis plan. The confirmatory analysis is performed for both the PP population and the ITT population. This approach reflects the equal importance of both analysis sets in a non-inferiority trial [29]. For the PP analysis missing values for the primary endpoint are not expected. In the ITT population missing values will be replaced according to Higgins [27]. As appropriate, a third population will be defined to adequately incorporate routinely collected data of patients who withdraw prematurely but gave informed consent for usage of routinely collected data. Details on inclusion of such data into sensitivity analyses of primary and secondary endpoints will be defined in more detail in the SAP. In case of uncertainty regarding data quality and reliablility these patients will only be analysed descriptively.

Additionally, binary logistic regression models will be performed as sensitivity analysis for the intervention comparison of the relapse rates adjusting for age, gender, center (grouped), and for results of therapeutic drug monitoring (grouped) based on different populations (PP, ITT, with values of drop-outs set to worst case).

All secondary outcomes will be evaluated descriptively, using appropriate statistical methods based on the underlying distribution of the data. Descriptive p-values are reported together with 95% confidence intervals for the corresponding effects. Descriptive statistics for continuous parameters and scores include number of non-missing observations, mean, standard deviation, median, minimum and maximum, performed for treatment groups as well as subgroups and overall. The description of categorical variables (ordinal or nominal) includes the number and percentage of patients belonging to the relevant categories in the study population as well as to each treatment group.

Rates of adverse and serious adverse events will be calculated with 95% confidence intervals for treatment group comparisons.

Statistical methods are used to assess the quality of the data, homogeneity of treatment groups, endpoints and safety of the two intervention groups. Details of the statistical analysis will be fixed at the latest in the Statistical Analysis Plan (SAP) to be prepared within the first year after start of patient recruitment. All persons taking part in the preparation of the SAP and possible

later changes to it will only have access to blinded data to avoid introduction of bias. All analyses will employ SAS Version 9.2 or higher.

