3 STUDY DESIGN AND DESCRIPTION

3.1 Study design

This is a prospective, randomized, multicenter, controlled, open, parallel group phase III study.

After initiation of the study, patients will be screened consecutively and eligible patients will be enrolled into the study at each center. To achieve comparable intervention groups and to minimize a potential selection bias, patients will be allocated in a concealed fashion by means of randomization using a centralized web-based tool (www.randomizer.at).

Each sites' principal investigator has to declare to the coordinating investigator/sponsor that he/she will conduct the study according to the protocol, ethical rules, and to provide the support as needed. To minimize a potential performance bias, this will be fixed in a contract prior to commencing the study. The clinical monitor will introduce the sites in detail to study procedures and documentation in advance.

Bias by potential influential factors will be addressed by inclusion as covariates into the statistical analysis. Independent clinical on-site monitoring to ensure patients safety and integrity of the clinical data in adherence to study protocol will focus on source data documentation, correctness of data, and adherence to study procedures, e.g. randomization and treatment.

Based on the performed interventions and planned analysis blinding is not feasible to minimize a detection bias, because the interventions can easily be differentiated due to visible side effects such as obesity, which is only expected in the control group. Furthermore, MMF is used in liquid form and prednisone as a tablet. The primary endpoint is based on standardized diagnostic work-up results, i.e. is an objective criteria.

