5.5 Randomization

5.5.1 Randomization method

All patients who seem suitable for study participation and take part in the screening, will be registered in a screening log and receive a screening number. Together with the center id this will be the unique identification number throughout the study. At the end of the screening phase the suitability of the patient is assessed finally.

When the patient is included in the study (all inclusion criteria fit and none of the exclusion criteria apply), he will be given a consecutive randomization number according to the randomization tool. Patients withdrawn from the study retain their number.

To achieve comparable intervention groups, patients will be allocated in a concealed fashion by means of randomization using a centralized web-based tool (www.randomizer.at). Randomization will be performed stratified by age groups (grouped: <7 years of age), because age is known to influence the occurrence of relapses. If the randomizer is not available in urgent cases the Institute of Medical Biometry and Informatics can be contacted ([name]) and a biometrician or data manager will perform the randomization.

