8.1 Sample Size Calculation

The sample size calculation is based on the primary efficacy endpoint "occurrence of treated relapse within 24 months after completion of the initial treatment". In the literature different information are given regarding the relapse rate for the control group receiving standard prednisone therapy. We have decided to assume a relapse rate of 51% according to Gipson et al. [8] which gives the worst case resulting in a conservative sample size estimation. The same rate is expected for the experimental group. If the relapse rate in the experimental group accounts to less than 15% above the relapse rate of the control group, this will be considered as clinically irrelevant based upon clinical judgment. Therefore the margin is set to δ =0.15. As the direction of the difference to be established is known for non-inferiority studies and as - due to the rareness of the disease and the related limited available number of patients - the study could otherwise not be performed with sufficient power, a one-sided significance level of 5% is applied. Testing at a one-sided significance level of α = 5% and aspiring a power of 80%, a total of 272 patients (136 per group) are required (calculations performed with AddPlan 6.0). To account for 10% drop-out rate and major protocol violations in a further 10% 340 patients will be randomized.

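### Randomisation is stratified by age because age affects relapse, but the confirmatory test is unstratified and the age-adjusted sensitivity model has no stated risk-difference output

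*Protocol*

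**What the plan says.** Protocol section 5.5.1: "Randomization will be performed stratified by age groups (grouped: <7 years of age), because age is known to influence the occurrence of relapses". No other stratification factor is named.

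Section 8.4 gives the confirmatory analysis. The hypotheses concern the difference in relapse rates, MMF minus prednisone, against 0.15, and non-inferiority "will be evaluated using the test according to Farrington and Manning [17". The test is run in the PP and ITT sets, which are described as equally important. No stratum or covariate is named.

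The only place where age is adjusted for is also in section 8.4: "binary logistic regression models will be performed as sensitivity analysis for the intervention comparison of the relapse rates adjusting for age, gender, center (grouped", together with grouped drug-monitoring results. The effect measure to be reported from these models is not stated.

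Section 3.1 makes a general commitment: "Bias by potential influential factors will be addressed by inclusion as covariates into the statistical analysis".

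Section 8.1 sizes the trial: "We have decided to assume a relapse rate of 51"% in both arms, "Therefore the margin is set to δ =0.15", "a one-sided significance level of 5% is applied", "aspiring a power of 80"%. This gives 136 per group, 272 in total and 340 randomised.

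**The concern.** A factor important enough to stratify randomisation is normally carried into the analysis. Stratified randomisation removes the between-age variation from the true sampling error of the treatment difference. The unstratified test still counts that variation in its standard error, so it is a little less powerful than it could be. Section 8.1 justifies the one-sided 5% level by the rarity of the disease, so power that costs nothing is worth taking.

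The second consequence concerns the PP set. Section 8.3 removes children after randomisation, for example for an interruption of more than 3 days. Section 5.4.7 sets out toxicity-driven pauses and discontinuations for MMF. Exclusions may therefore differ by arm and by age, and the balance created by stratified randomisation is not guaranteed in a set with equal confirmatory weight. The test as written cannot correct such an imbalance, and the model that could do so is not tied to the margin.

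**Working it through.** **1. Inputs.** From sections 8.1 and 8.4: relapse 0.51 in both arms, margin 0.15, one-sided 5%, power 80%, n = 136 per arm. Not in the protocol, so assumed: share of children under 7, s = 0.70 to 0.80; relapse gap between age groups, g = 0.10 to 0.25; overall relapse held at 0.51.

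**2. The plan's own figure.** The Farrington-Manning restricted rates are 0.585 and 0.435. Then n = [(1.645·√0.4886 + 0.842·√0.4998)/0.15]² = 135.3, so 136 per group and 272 in total; 272/0.80 = 340. The stated size reproduces exactly with the unstratified formula.

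**3. Power, like for like** (normal approximation, unpooled variance, arms balanced on age).
- Total variance per child: 0.51 × 0.49 = 0.2499.
- Between-age part: s(1−s)g². Within-age part: W = 0.2499 − s(1−s)g².
- Standard error the unstratified test uses: √(2 × 0.2499/136) = 0.0606. True standard error, also used by the stratified test: SE = √(2W/136).
- Unstratified power: Φ[(0.15 − 1.645 × 0.0606)/SE]. Stratified power: Φ[0.15/SE − 1.645].

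| s | g | W | SE | unstratified | stratified | gain (points) |
|---|---|---|---|---|---|---|
| 0.80 | 0.10 | 0.2483 | 0.0604 | 79.7% | 79.9% | 0.15 |
| 0.80 | 0.25 | 0.2399 | 0.0594 | 80.1% | 81.1% | 0.9 |
| 0.70 | 0.10 | 0.2478 | 0.0604 | 79.8% | 80.0% | 0.2 |
| 0.70 | 0.25 | 0.2368 | 0.0590 | 80.3% | 81.5% | 1.2 |

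**4. Type I error with balanced arms.** The exact size of the unstratified test at the margin (136 per arm) is 0.054 with no age effect. It falls as the gap widens, to 0.046-0.049 at a 30-point gap (60-80% under 7). Ignoring the strata does not raise the error.

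**5. Age imbalance in the PP set.** Bias in the unstratified risk difference = (difference between arms in the share under 7) × g. With g = 0.20, an imbalance of 5 points gives 0.01 and one of 10 points gives 0.02.
- Bias favouring MMF, true difference 0.15: the standard error is √[(0.66 × 0.34 + 0.51 × 0.49)/136] = 0.0591. The error is Φ(−1.645 + 0.01/0.0591) = 7.0%, or 9.6% with 0.02.
- Bias against MMF, true difference 0: power is Φ[(0.15 − 0.01)/0.0606 − 1.645] = 74.7%, or 69.1% with 0.02, against 79.7% without bias.

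How large is the assumed imbalance? Take 170 randomised and 136 retained per arm, 75% under 7 (128 of 170), and the control arm losing children in proportion. If the MMF arm loses 19 younger and 15 older children, 109/136 = 80% are under 7, an imbalance of 5 points. If it loses 12 and 22, 116/136 = 85%, an imbalance of 10 points, but over half of its 42 older children are gone. So 5 points needs a marked pattern of exclusions and 10 points is an extreme case.

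**6. Scale of the logistic model.** A 15-point margin equals an odds ratio of (0.66/0.34)/(0.51/0.49) = 1.87 at a control rate of 51%, 1.91 at 30% and 2.00 at 60%. An odds ratio alone has no fixed counterpart to 0.15. A risk difference standardised from the same model does.

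**The case against.** The strongest reply is that the plan is coherent as it stands. A prespecified, unstratified risk-difference test addresses the stated hypotheses directly, matches the test used for sizing, and is backed by an age-adjusted sensitivity analysis in both sets. The gain from stratifying is around one point of power at most, and every figure rests on an age mix and an age gap that the protocol does not give. All of this stands. It limits the point to a free improvement; it does not remove it.

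Four stronger readings are tempting, and the protocol does not support them.
- A reader might infer that the logistic model cannot be compared with the margin. Section 8.4 never specifies an odds ratio, and a logistic model can yield a standardised risk difference. The analysis plan, not seen here, may already ask for one.
- A reader might infer that the commitment in section 3.1 is broken. It refers to the statistical analysis in general, not to the confirmatory test, and the sensitivity model meets it.
- A reader might set stratified power against 80.2%, the Farrington-Manning power with no age effect, and obtain 80.4-82.0%. That comparison overstates the gain, because stratified randomisation raises the power of the unstratified test as well.
- A reader might infer that the unstratified test is invalid. With balanced arms it is not: its size falls as the age effect grows.

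The PP error rates in step 5 also describe that analysis alone. If the claim requires success in both sets, the ITT test still limits a false claim of non-inferiority. A bias against MMF in the PP set would cost the trial power all the same.

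**Conclusion.** The point holds as a modest one. The protocol uses age in the design for a stated prognostic reason and leaves it out of the analysis that decides the trial. The confirmatory test remains valid when the arms are balanced on age, becomes slightly conservative when the age effect is large, and the 272 needs no change.

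Two costs remain. One is a power loss of about 0.15 to 1.2 points, assuming 70-80% under 7 and a 10-25 point gap. The other is an uncorrected bias in the PP analysis equal to imbalance times gap: 1-2 points under an assumed 5-10 point imbalance and a 20-point gap. That moves the nominal 5% error of the PP analysis to about 7-10%, or its power to about 75-69%, depending on direction. The second cost is the better reason to act, although the upper end of its range needs an extreme pattern of exclusions. Stratifying removes only the part of any PP selection that runs through age group.

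**What to change.** Make the confirmatory analysis, in both the PP and ITT sets, a risk difference stratified by the age group used at randomisation: Mantel-Haenszel weights, a stratified Farrington-Manning or Miettinen-Nurminen test against 0.15 at one-sided 5%, and the matching two-sided 90% confidence interval. Keep the unstratified Farrington-Manning test as a sensitivity analysis. Report the logistic sensitivity model as a standardised (marginal) risk difference with its interval, so that it can be read against 0.15.

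Because section 8.4 names the confirmatory test, the change must be prespecified before database lock, preferably by protocol amendment as well as in the analysis plan. The cost is wording and programming. The age stratum is known for every randomised child, no new data are needed, and the sample size is unchanged.

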The persons having care and custody of the child are instructed to interpret the results of the Albustix[®] and are instructed to react as described. In doubt the persons having care and custody of the child are encouraged to contact the study center early.

Albustix™	Interpretation	Consequence
Negative	No relapse	Nothing to do
Trace		
30 mg/dL = +	doubtful value	 Daily weight investigation for edema (yes/no) The urine protein/creatinine ratio (Up/c) or a specimen of a urine collection has to be analyzed, if 1+ appears for 3 days or 1+ is combined with ≥2+ within 3 days.
100 mg/dL = ++		
300 mg/dL = +++	Relapse, if detected on 3 consecutive days	Contact study center
≥2000 mg/dL		
= ++++		

Visit 2

Visit 2 is scheduled at 4 weeks after visit 1 (± 5 days).

At visit 2, the history since visit 1 is documented, especially if one or more relapses occurred since visit 1.. In case of a relapse, date of first day of relapse (definition fulfilled) is documented. For each relapse, it is documented, according to which criteria the relapse was diagnosed: Albustix $\geq 2+$ (>30mg/dL) for 3 consecutive days, Spot urine: Up/c ratio ≥ 2 g/g, or collecting urine: Up excretion of ≥ 40 mg/m² BSA/h. If the relapse was treated, the medication is recorded. Further, date of remission is documented (see definitions). In order to document possible trigger factor infections during relapse (e.g. respiratory tract infection, gastroenteritis) and vaccinations within two weeks prior to the relapse are recorded, too. All information from the diary (days missing school attendance, days of hospitalization since last visit are recorded. According to diary and patients inquiry adherence to study medication is assessed (Reduction of study medication > 50%?, Pause of study medication > 3 days?).

Side effects of the treatment are retrieved in yes/no manner (Behavioral disturbances since visit 1: child feels sad, anxious, irritable, as well as euphoric state, aggressive state, nausea, vomiting (defined as a frequency of more than 1 times per day), diarrhea (defined as a frequency of more than 4 loose stools daily), headache, muscle weakness, any new infection).

Application of any current medication (other than immunosuppressive agents) is documented.

The event of renal biopsy since last visit is recorded with histology.

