The physical examination contains investigation of the skin in yes/no manner (acne, cushingoid facies, striae, and hypertrichosis), further pathological organ-specific findings in yes/no/not done manner (lymphadenopathy, pharyngitis, otitis media, heart murmur, arrhythmia, respiratory tract infection, abdominal pain, and muscle weakness) and pubertal status.

Measurement of weight, height (BMI is computed) and blood pressure after 3 minutes rest are done and documented.

A sample of spot urine is analyzed with dip stick (Albustix®) and quantitatively for creatinine, protein, albumin in the laboratory of the study center (urine protein/creatinine ratio is computed).

The blood test contains: blood cell count (leukocytes, erythrocytes, hemoglobin, and thrombocytes), HbA_{1c}, creatinine, blood urea/blood urea nitrogen (BUN), uric acid, calcium, phosphate, alkaline phosphatase, 25-OH Vitamin D, total protein, albumin, GPT/ALT, IgG, IgE, Cholesterol.

Study specific investigations are, if treated with MMF:

Therapeutic drug monitoring of mycophenolic acid (TDM MPA)

- Therapeutic drug monitoring of mycophenolic acid (TDM MPA) is optional and should be performed, if possible due to local facilities. These data will be helpful for retrospective analysis.
 - The blood test of visit 2 is schedulded before taking MMF.
 - For taking blood, an indwelling venous cannula is inserted in order to reuse it after 60 and 120 minutes without pain.
 - Intake of MMF is immediately after taking blood sample
 - Blood is drawn from the indwelling venous cannula after 60 and 120 minutes
 - For every sample 1,2 ml EDTA blood is necessary
 - Centrifugate EDTA blood
 - Plasma should be stored at -20°C
 - Tube is labeled with ID, number of TDM and time (0 min, 60 min or 120 min)
 - All samples could be sent (adress see below) together
 - Samples have to be sent on dry ice
- o Plasma is sent to

University Cologne

Pharmakologisches Institut

[name]

[name]

[contact] [contact]

E-Mail: [contact]

The level of mycophenolic acid (MPA) in plasma before and 60 minutes as well as 120 minutes after intake of mycophenolate mofetil will be analyzed centrally and interpreted retrospectively. Therefore, the study centers will not be informed about the results and dosage of mycophenolate mofetil will not be adjusted.

Visit 3

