Visit 3 is scheduled at 11 weeks (± 7 days) after day 1 (= first day of treatment with standard therapy for first episode of idiopathic nephrotic syndrome in children).

At visit 3, the history since visit 2 is documented, especially if one or more relapses occurred since visit 2. In case of a relapse, date of first day of relapse (definition fulfilled) is documented. For each relapse, it is documented, according to which criteria the relapse was diagnosed: Albustix $\geq 2+$ (>30mg/dL) for 3 consecutive days, Spot urine: Up/c ratio ≥ 2 g/g, or collecting urine: Up excretion of ≥ 40 mg/m² BSA/h. If the relapse was treated, the medication is recorded. Further, date of remission is documented (see definitions). In order to document possible trigger factor infections during relapse (e.g. respiratory tract infection, gastroenteritis) and vaccinations within two weeks prior to the relapse are recorded, too. All information from the diary (days missing school attendance, days of hospitalization) since last visit are recorded. According to diary and patients inquiry adherence to study medication is assessed (Reduction of study medication > 50%?, Pause of study medication > 3 days?).

Side effects of the treatment are retrieved in yes/no manner (Behavioral disturbances since visit 2: child feels sad, anxious, irritable, as well as euphoric state, aggressive state, nausea, vomiting (defined as a frequency of more than 1 times per day), diarrhea (defined as a frequency of more than 4 loose stools daily), headache, muscle weakness, any new infection).

Application of any current medication (other than immunosuppressive agents) is documented.

The event of renal biopsy since last visit is recorded with histology.

The physical examination contains investigation of the skin in yes/no manner (acne, cushingoid facies, striae, and hypertrichosis), further pathological organ-specific findings in yes/no/not done manner (lymphadenopathy, pharyngitis, otitis media, heart murmur, arrhythmia, respiratory tract infection, abdominal pain, and muscle weakness) and pubertal status.

Measurement of weight, height (BMI is computed) and blood pressure after 3 minutes rest are done and documented.

A sample of spot urine is analyzed with dip stick (Albustix®) and quantitatively for creatinine, protein, albumin in the laboratory of the study center (urine protein/creatinine ratio is computed).

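### Section 8.4 adjusts the between-arm logistic sensitivity model for mycophenolic acid drug levels, which only MMF-treated children can have, so its arm coefficient is not the randomised contrast

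*Protocol*

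**What the plan says.** Section 8.4 makes the Farrington-Manning test, described without covariates, the confirmatory analysis in both the PP and ITT populations. It then adds that "binary logistic regression models will be performed as sensitivity analysis for the intervention comparison of the relapse rates". The covariate list for these models reads "adjusting for age, gender, center (grouped), and for results of therapeutic drug monitoring (grouped", and the analysis sets are given as "based on different populations (PP, ITT, with values of drop-outs set to worst case". The stated purpose is the contrast between arms, and grouped TDM is one of four named covariates.

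Section 6.1 describes the TDM data under visit 2 and again under visit 3:

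- **Who has it.** The procedure is introduced with "Study specific investigations are, if treated with MMF". No TDM is described for prednisone children.
- **What it is.** "The level of mycophenolic acid (MPA) in plasma before and 60 minutes as well as 120 minutes after intake of mycophenolate mofetil" is what gets analysed, so the quantity is undefined without MMF.
- **How complete it is.** "Therapeutic drug monitoring of mycophenolic acid (TDM MPA) is optional and should be performed, if possible due to local facilities".
- **When it is taken.** Visit 1 is the randomisation visit. "Visit 2 is scheduled at 4 weeks after visit 1", and "Visit 3 is scheduled at 11 weeks (± 7 days) after day 1". Both measurements are taken on treatment and after randomisation.

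Nothing in the protocol limits the TDM term to a model within the MMF arm.

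**The concern.** A covariate in a treatment-comparison model has to be defined in both arms and should be fixed before randomisation. TDM is neither. Every control child lacks a value by design, some MMF children lack one because of where they are treated, and the value that exists follows from receiving MMF.

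What is at stake is the usefulness of this model. Section 3.1 says that bias from influential factors will be handled by including covariates in the analysis, and section 8.4 is the only place that names any. Randomisation is stratified by age (section 5.5.1) and the primary test is described without covariates, so this is also the only stated adjustment for age. If the arm coefficient does not estimate the randomised difference, the model can neither support nor contradict the primary result in this open-label trial.

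**Working it through.** **The plan's own figure.** The sample size does not depend on this model. With the section 8.1 inputs (51% relapse in both arms, margin 0.15, one-sided 5%, 80% power), the Farrington-Manning formula gives 135.3, rounded up to 136 per arm and 272 in total. 272 / 0.80 = 340 randomised. Both match the protocol.

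**Step 1: which coefficient each coding leaves.** Take 170 children per arm (section 4.1), an intercept, an arm indicator, one baseline indicator (age) and three TDM groups. The number of groups is an assumption. Adding gender and center does not remove the deficiency.

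| Coding of TDM | Columns / rank | What the arm coefficient is |
|---|---|---|
| Complete cases only | 5 / 4 | Not estimable: all controls are dropped and arm is constant |
| Controls as their own category, all MMF children measured | 6 / 5 | Aliased: the three TDM indicators sum to the arm indicator. If software drops one, arm becomes that exposure group versus all controls |
| Controls placed in one TDM group | full rank | That one MMF exposure group versus all controls |
| Controls share a not-measured group with unmeasured MMF children | 6 / 6 | Unmeasured MMF children versus all controls |

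The second row also applies if unmeasured MMF children have a category separate from controls. These results follow from the design and need no assumed relapse rate.

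**Step 2: how far the coefficient can move (illustration).** The protocol gives no relapse rates by exposure, so these are assumptions. Overall relapse is 51% in both arms, so the true odds ratio is 1.00. The control odds are 0.51/0.49 = 1.041. The arm coefficient compares the exposure group that shares the reference with controls.

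- *No exposure-response (51% in every group):* odds ratio 1.00 whichever group is the reference.
- *Halves at 61% and 41%:* (0.61/0.39)/1.041 = 1.50, or (0.41/0.59)/1.041 = 0.67.
- *Thirds at 66%, 51%, 36%:* (0.66/0.34)/1.041 = 1.87 with the low-exposure group as reference, or (0.36/0.64)/1.041 = 0.54 with the high-exposure group. Simulated logistic fits (1000 runs each) gave 1.86 and 0.54.

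**Step 3: precision.** Without TDM, the standard error of the log odds ratio is √[2/(170 × 0.51 × 0.49)] = 0.217 (simulated 0.218, mean log odds ratio 0.00). With one third of the MMF arm as the effective comparison group, it rises to about 0.32 in the 66/51/36% example.

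**Step 4: the shared not-measured group.** If 30% to 70% of MMF children are measured (assumption), the simulated standard error is 0.24 to 0.32. The estimate centred on the true value, but only because measurement was simulated as random. In the protocol it depends on local facilities. Under section 4.4.1, children taken off MMF for adverse events receive the standard treatment and stay in follow-up, so the ITT set can contain MMF-arm children without TDM for reasons connected with treatment.

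**The case against.** The strongest reply has four parts.

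1. **Only a supportive analysis is affected.** No success criterion uses these models. This stands, and it limits the severity.
2. **A valid contrast can still be recovered.** If controls form their own group and all MMF children are measured, the size-weighted average of the MMF groups against control is estimable. In the thirds example the mean MMF logit is (0.663 + 0.040 − 0.575)/3 = 0.043 against 0.040 for control, an odds ratio of about 1.00. The arithmetic is right, so a comparison of the arms can be extracted from such a fit. But the protocol specifies no such contrast, it is not the arm coefficient, and with it the TDM term contributes essentially no adjustment.
3. **Coding is a matter for the SAP.** Coding is, but the choice of TDM as a covariate in the between-arm model is already fixed in section 8.4. That is a wrong statement, not missing detail.
4. **TDM may have been meant for a model within MMF children.** Section 6.1 does present the data as useful for later retrospective analysis, which fits that reading. Section 8.4 says otherwise.

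**Conclusion.** The point holds with moderate severity. As written, the model gives an arm coefficient that is either not estimable or compares an MMF subgroup with all controls, so it cannot serve as a check on the primary result. This rests only on TDM being confined to MMF children, optional and post-randomisation, all of which the protocol states.

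Four stronger readings are tempting, and the protocol does not support them:

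- *That the trial's main conclusion is at risk.* The Farrington-Manning test uses no TDM data, and 272/340 is unaffected.
- *That arm is always collinear with TDM.* This fails when unmeasured MMF children share the controls' category. The model is then full rank, and the fault is the subgroup comparison.
- *That the bias has a known size, or a known fraction of the 0.15 margin.* The shifts in the working rest on assumed rates and on reading a reference-group coefficient, and they vanish without an exposure-response relation. The margin is a risk difference for the primary test, and the protocol gives no odds-ratio margin.
- *That adjustment shrinks the treatment effect.* The shift can go in either direction, and attenuation has not been shown.

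**What to change.** In section 8.4, delete therapeutic drug monitoring from the covariates of the treatment-comparison models and keep the baseline variables: age, gender and grouped center. Add that mycophenolic acid exposure will be related to relapse in a separate, exploratory model restricted to MMF-treated children with TDM results, with the number and proportion measured reported.

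The cost is one sentence in the protocol, carried into the SAP. It needs no new data, changes neither the primary test nor the sample size, and loses nothing from the TDM data already planned.
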